Scheduling Window Days	-	-	+2	+/-1	+/-3	-3 to +7	+/-6	+2	-1	+7	-
Dispensing and collecting of study drug, confirmation for number of study drug		x								x	x
Issuing, collecting and confirming the medication diary (oral administration)		x								x	x
Assessment of overall response (including clinical response, radiological response, and mycological response) 					xx	x	xx	x	x		
Adverse Events Monitoring		← Continuing to confirm →									x

x: must be done

xx: will be done as needed

1. Procedure must be done before the initiation of study therapy. If conducted on a same date, measurement and evaluation is not needed 2 times.
2. 12-lead ECG is tried to perform at the timing of maximum serum drug concentration. Recommended timing is as follows;
  - MK-5592 IV solution: just after the end of treatment
  - MK-5592 solid oral tablet: 3 to 5 hours after the treatment
  - Voriconazole IV: just after the end of treatment
  - Voriconazole oral tablet: 1 to 2 hours after the treatment
3. Subjects enrolled with a part of these testings, mycology testing and mycological serology testing (aspergillus antigen, antibody and β-D-glucan) must be performed. Mycological testings must be performed during the treatment and EOT excluding eradication of the sample enable to collect. Aspergillus antibody is performed for the subject with chronic pulmonary aspergillosis and is performed at the screening only. Serology testing is no need for subjects with Zygomycosis and Fusariosis
4. Data comes from within 7 days before initiation of study therapy, it can be used as a screening result. For the mycology test (culture testing, direct microscopy or histopathological examination etc.), data comes from within 14 days before initiation of study therapy can be used as a screening result. Aspergillus antibody testing, data comes from within 28 days before initiation of study therapy can be used as a screening result. Mycology test shroud be done by following 7.1.2.6 Mycology Testing and the isolated fungus should be provided to the central laboratory.
5. Only for the subject with invasive aspergillosis.
6. Intravenous treatment (The plasma samples for PK evaluation in the subjects with zygomycosis during the extension period will not be needed)

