  - a: Day 1;30 minutes before the treatment, just before the first treatment, 6 to 10 hours after the initiation of the infusion and just before the treatment of second infusion. Blood sampling after the treatment on Day 1 (just before the end of first infusion, 6 to 10 hours after the initiation of the infusion and just before the treatment of second infusion) can be performed after the second dosing if it is difficult to perform the blood sampling after the first dosing.
  - b: Day 3, Day 14, Day 28, Day 42 and end of treatment; 30 minutes before the treatment
  - c: Day 8; 30 minutes before the treatment, just before the end of infusion, 2 to 3 hours after the initiation of infusion, 8 to 10 hour after the initiation of treatment and 30 minutes before the next day treatment.
  - d: At the time of interruption or discontinuation due to adverse events, or at the incidence of serious adverse events by MK-5592 administration.

7. Oral administration (The plasma samples for PK evaluation in the subjects with zygomycosis during the extension period will not be needed)
  - a: Day 1; 30 minutes before the treatment, 2 to 4 hour after the first treatment, 6 to 10 hours after the treatment and just before the second treatment. Blood sampling after the treatment on Day 1 (2 to 4 hours after the first treatment, 6 to 10 hours after the treatment and just before the second treatment) can be performed after the second dosing if it is difficult to perform the blood sampling after the first dosing
  - b: Day 3, Day 14, Day 28, Day 42 and end of treatment; 30 minutes before the treatment
  - c: Day 8; 30 minutes before the treatment, 2 to 3 hour after the treatment, 4 to 6 hours after the treatment, 8 to 10 hour after the treatment and 30 minutes before the next day treatment.
  - d: At the time of interruption or discontinuation due to adverse events, or at the incidence of serious adverse events by MK-5592 administration.
  - e: After 7 days of switching formulation; 30 minutes before the treatment and 2 to 6 hour after the treatment (only for the subject who switch from IV to oral)

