11. At the switching formulation (from IV to PO), investigator must evaluate the overall response (including clinical response, radiological response, and mycological response). Data conducted on the day of switching formulation or preceding day can be used as an overall response at the switching formulation. In case that subject who started using oral formulation cannot continue to receive the oral formulation during the treatment, investigator must evaluate the overall response at that time and conduct the discontinuation procedure [However, if the subject is a patient with zygomycosis and joins the extension period, the switch of the formulation(iv↔tablet) could be done based on the subject's condition but dose modification of MK-5592 must not be allowed and the investigator does not need to evaluate the overall response at the timing of switching the formulation].
12. Weight measurement and Treatment Allocation may be conducted between Day -1 and Day 1. Treatment allocation and weight measurement should be conducted on the same date. Weight used for treatment allocation should be considered as basis of the dosing calculation. When conducting the Visit 2 weight measurement on Day -1, weight measurement does not need to be repeated on Day 1.
13. As a general rule, treatment duration of all disease is 84 days (77-84 days with considering the treatment allowance). At the EOT (completion and discontinuation) visit before the transition to the extension period, procedure other than dose administration should be conducted within EOT +2 days. At the end of treatment or discontinuation, procedure at EOT should be conducted before starting other systemic antifungal therapy[However, if the subject is a patient with zygomycosis and joins the extension period, procedure at visit 12/EOT does not need to be conducted at the last dose of MK-5592 therapy in the extension period].
14. Informed Consent could be obtained prior 28 days of Day 1.
15. Urine pregnancy testing can be conducted. Even though urine pregnancy testing is conducted, serum pregnancy testing should be conducted as a screening testing.

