#### **7.1.2.4 12-Lead Electrocardiogram**

12-lead electrocardiogram is performed using standard equipment that can be measured for ventricular rate, RR, PR, QRS, QT and QTc interval. 12-lead electrocardiogram is performed at the scheduled or unscheduled visit and tried to measure at the time of the highest plasma concentration. Serum electrolytes (K, Ca, Mg) must be measured on the same day and recorded in the source document and eCRF, in case an unscheduled 12-lead electrocardiogram is performed. Clinically abnormal findings in the electrocardiogram will be followed up until recovering to the baseline value or stabilization appropriately. If QTc interval is greater than 500 msec, study treatment must be discontinued.

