#### 8.2.5.2 Statistical Methods for Safety Analyses

Safety and tolerability will be assessed by clinical review of all relevant parameters including adverse experiences (AEs), laboratory tests, vital signs, and ECG measurements.

The analysis of safety results will follow a tiered approach ([Table 27](#)) but tier 1 events are not defined in this protocol. The tiers differ with respect to the analyses that will be performed. Membership in Tier 2 requires that at least 4 patients in any treatment group exhibit the event; all other adverse experiences and predefined limits of change will belong to Tier 3. In addition, the broad clinical and laboratory AE categories consisting of the percentage of patients with any AE, a drug related AE, a serious AE, an AE which is both drug-related and serious, and who discontinued due to an AE will be considered Tier 2 endpoints. Tier 2 parameters will be assessed via point estimates with 95% confidence intervals provided for between-group comparisons; only point estimates by treatment group are provided for Tier 3 safety parameters.

The threshold of at least 4 events was chosen because the 95% confidence interval for the between-group difference in percent incidence will include zero when both treatment groups have less than 4 events and thus would add little to the interpretation of potentially meaningful differences. Because many 95% confidence intervals may be provided without adjustment for multiplicity, the confidence intervals should be regarded as a helpful descriptive measure to be used in review, not a formal method for assessing the statistical significance of the between-group differences in adverse experiences and predefined limits of change.

Continuous measures such as changes from baseline in laboratory, vital signs, and ECG parameters will be considered Tier 3 safety parameters. Summary statistics for baseline, on-treatment, and change from baseline values will be provided by treatment group in table format.

Table 27 Analysis Strategy for Safety Parameters

Safety Tier	Safety Endpoint †	p-value	95% CI for Treatment Comparison	Descriptive Statistics
Tier 1	Not defined in this protocol	X	X	X
Tier 2	Any AE		X	X
	Any Serious AE		X	X
	Any Drug-Related AE		X	X
	Any Serious and Drug-Related AE		X	X
	Discontinuation due to AE		X	X
	Specific AEs, SOCs, or PDLCs (incidence $\geq 4$ of patients in one of the treatment groups)		X	X

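### The end-of-treatment ECG may be taken up to 2 days after dosing ends, and the SAP does not separate such readings from on-treatment ones

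*Combined protocol and SAP*

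**What the plan says.** **Timing aim.** Section 6.0, footnote 2: "12-lead ECG is tried to perform at the timing of maximum serum drug concentration". Section 7.1.2.4 repeats the aim: "tried to measure at the time of the highest plasma concentration". Footnote 2 gives a recommended time for each drug and formulation. For either IV product it is just after the infusion. For the tablets it reads "MK-5592 solid oral tablet: 3 to 5 hours after the treatment" and "Voriconazole oral tablet: 1 to 2 hours after the treatment".

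**Visit window.** The flow chart requires an ECG at Visit 12 (EOT or discontinuation), scheduled for Day 84 with a +2 day window. Footnote 13 adds that "procedure other than dose administration should be conducted within EOT +2 days", for completion and discontinuation alike, and makes no exception for the ECG.

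**Other ECGs.** The ECG row also marks Screening, Days 1, 3, 8 and 42, the day of a formulation switch, and Visit 13, which is 14 days after the end of treatment.

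**Analysis.** Section 8.2.5.2 puts changes in ECG parameters in Tier 3. "Summary statistics for baseline, on-treatment, and change from baseline values will be provided by treatment group", with no definition of on-treatment in terms of time since the last dose.

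**The concern.** An ECG can be aimed at peak concentration only on a day when a dose is given. An EOT ECG done 1 or 2 days after the last dose has no dose to follow, so it is taken after dosing has ended and away from peak. It would still enter the on-treatment summary under the EOT label.

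This reading is the only routine one of its kind. Between Day 42 and Day 84, nominally half of the 84-day treatment period (84 − 42 = 42 days), no other on-drug ECG is scheduled unless the subject switches formulation. Visit 13 already supplies the post-treatment reading, so a late EOT ECG loses the late on-drug value.

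The two arms also have different dosing intervals, so the same visit label can stand for different exposure. The primary objective is to assess and compare safety, and the trial tests no hypothesis, so the descriptive tables carry the ECG comparison.

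**Working it through.** The plan states no figure to reproduce here. The check is interval arithmetic, followed by a bound on what exposure might remain.

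**1. Which clock applies.** I count 2 days from the last dose. Footnote 13 counts from EOT, and its exemption for the extension period, "procedure at visit 12/EOT does not need to be conducted at the last dose of MK-5592 therapy in the extension period", implies that EOT otherwise attaches to the last dose. If Day 84 +2 were instead applied to a subject whose last dose was Day 77 (the lower end of the 77-84 day allowance), the gap could be 86 − 77 = 9 days. I do not rely on that reading.

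**2. Position of a late ECG within the dosing schedule.** Inputs: MK-5592 is given every 24 h from Day 2, with 21-27 h allowed (Sections 5.2.1.1.1 and 5.2.1.1.2). Voriconazole is given every 12 h, with 9-15 h allowed (Sections 5.2.1.1.3 and 5.2.1.1.4).

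| Time since last dose | MK-5592 | Voriconazole |
|---|---|---|
| 24 h | 24/24 = 1 interval; 27 − 24 = 3 h inside the limit | 24/12 = 2 intervals; 24 − 15 = 9 h past the limit |
| 48 h | 48/24 = 2 intervals; 48 − 27 = 21 h past the limit | 48/12 = 4 intervals; 48 − 15 = 33 h past the limit |

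At 24 h the MK-5592 reading is an ordinary trough with no dose overdue. The voriconazole reading is already outside its permitted interval. This difference follows from the protocol's own intervals and needs no pharmacokinetic assumption.

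**3. What might remain in plasma.** The documents give no elimination half-life for either drug, so the values below are assumptions. Remaining fraction = 0.5^(t / half-life).

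| Assumed half-life | 24 h | 48 h |
|---|---|---|
| 6 h | 6% | 0.4% |
| 12 h | 25% | 6% |
| 24 h | 50% | 25% |
| 36 h | 63% | 40% |
| 48 h | 71% | 50% |

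For MK-5592 the Table 6 regression, pCavg = 228 + 1.02 × Cmin, offers a rough bound. At Cavg 1580 ng/mL (Table 5, 300 mg pooled), Cmin = (1580 − 228)/1.02 = 1325 ng/mL, which is 84% of the average. In a one-compartment bolus model, Cmin/Cavg = x/(e^x − 1) with x = k × 24 h. That gives a half-life of about 49 h, with about half of peak left at 48 h. At Cavg 981 the same steps give Cmin 738, a ratio of 0.75, a half-life of about 31 h and 34% left. These half-lives are upper bounds. They suggest that substantial MK-5592 could remain at 48 h. Nothing comparable can be derived for voriconazole.

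**4. What the SAP does with the reading.** Section 8.2.4.2 sets a post-dose condition for laboratory and vital-sign measurements, and Section 8.2.5.2 uses the on-treatment label. Neither limits the time between last dose and ECG, so a 48 h reading is not kept out.

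**The case against.** **Peak timing is best effort.** This stands. The wording is that sites try, at recommended times. Footnote 2 is attached to the whole ECG row, including Screening and Visit 13, where no peak is possible, so it cannot be a condition that every ECG must meet. A reader might infer a flat contradiction between footnotes 2 and 13; the text does not go that far. It leaves an aim that cannot be pursued on some of the days the window allows.

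**EOT is planned on a dosing day.** Largely true in the MK-5592 arm. The PK schedule reads "Day 3, Day 14, Day 28, Day 42 and end of treatment; 30 minutes before the treatment", and footnote 9 gives a fallback for early discontinuation, so the PK sample is already dealt with. That anchor does not exist in the voriconazole arm, which has no such sample, and in neither arm does it bind the ECG. How many EOT ECGs would be late is unknown.

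**The QTc stopping rule.** A reader might infer that late ECGs weaken the rule at QTc above 500 msec. They do not: the rule stops treatment, and by then dosing has ended.

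**Nothing is formally compared.** ECG change from baseline is Tier 3, with no between-arm interval or p-value, and the SAP names no separate EOT ECG table. This limits the impact. It does not make an undefined on-treatment label harmless.

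**A blanket rule would misclassify.** Fair. Calling every ECG after the last dosing day post-treatment would relabel MK-5592 readings still inside a normal interval. The fix therefore uses each drug's permitted interval.

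**Conclusion.** The point holds as a gap of modest size. The protocol permits an EOT ECG after dosing has ended and away from peak, and the SAP would report it among on-treatment values. Exposure at that reading can differ by arm: at 24 h, 3 h inside the permitted interval for MK-5592 and 9 h past it for voriconazole. This assumes that EOT is the day of the last dose.

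Two stronger conclusions are tempting and unsupported. One is that late EOT ECGs are off drug; the regression in the documents points the other way for MK-5592. The other is that the EOT summary favours the faster-clearing drug by some number of milliseconds. That would need both half-lives and a concentration-QTc relation, and the documents give none of these. Dosing frequency is not a substitute for clearance.

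The ECGs on Days 1, 3, 8 and 42 are untouched. What is at risk is the one routine on-drug reading after Day 42 and the meaning of the on-treatment label for EOT and discontinuation ECGs.

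**What to change.** 1. In Section 6.0, footnote 13, exclude the 12-lead ECG from the +2 day allowance for planned completers, so that it is taken on a dosing day at the footnote 2 times.
2. Record time since last dose for every EOT or discontinuation ECG.
3. In Section 8.2.5.2, summarise EOT and discontinuation ECGs taken after the last permitted dosing interval for that drug (beyond 27 h for MK-5592, beyond 15 h for voriconazole) separately from on-treatment values, and keep them in the safety tables.

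The PK sampling rules need no change. The cost is one footnote amendment, one recorded time and one SAP sentence. Booking becomes slightly tighter for completers, and some discontinuing subjects will have no on-treatment EOT ECG, although their reading is still reported.

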#### 4.2.3.3 Pharmacokinetic Endpoints

Steady-state pharmacokinetic profile of MK-5592 in Japanese patients with mycosis will be explored using population PK approach. The PPK analysis plan will be prepared separately.

*For MK-5592 treatment arm, plasma samples for PK evaluation will be collected at the following time points:*

For IV administration: Thirty minutes before the treatment, just before the end of first infusion, 6 to 10 hours after the initiation of the infusion and just before the treatment of second infusion on Day 1[Blood sampling after the first dosing on Day 1 (or second dosing) should be performed at least 3 hours apart among these sampling points (6 to 10 hours after the treatment and just before the second treatment)]. Thirty minutes before the treatment on Day 3, 14, 28, 42 and end of treatmenta, b. Thirty minutes before the treatment, just before the end of the infusion, 2 to 3 hours after the initiation of infusion, 8 to 10 hours after the initiation of infusion on Day 8 and thirty minutes before the treatment of the next day (on Day 9).

For oral administration: Thirty minutes before the treatment, 2 to 4 hours after the first treatment, 6 to 10 hours after the treatment and just before the second treatment on Day 1[Blood sampling after the first dosing on Day 1 (or second dosing) should be performed at least 3 hours apart among these sampling points (6 to 10 hours after the treatment and just before the second treatment)]. Thirty minutes before the treatment on Day 3, 14, 28, 42 and end of treatmenta, b. 30 minutes before the treatment and 2 to 6 hours after the treatment on after 7 days of switching formulation (Only for the subjects who switch from IV to orala). Thirty minutes before the treatment, 2 to 3 hours after the treatment, 4 to 6 hours after the treatment, 8 to 10 hours after the treatment on Day 8 and 30 minutes before the treatment of the next day (on Day 9).

[figure not shown]
For both formulations: At the time of interruptiona or discontinuationa due to adverse events, or at the incidence of serious adverse eventsa by MK-5592 administration.

a: The plasma samples for PK evaluation in the subjects with zygomycosis during the extension period will not be needed.

b: The plasma samples for PK evaluation in the subjects with zygomycosis must be collected at EOT before the transition to the extension period.

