#### 5.2.1.1.1 MK-5592 IV Solution

[Table 15](#) provides the dosing of MK-5592 for subjects randomized to the MK-5592 treatment arm if on IV therapy.

MK-5592 IV infusions will be prepared in 5% dextrose in water or saline. See the procedure separately for detail of MK-5592 IV formulation preparation. MK-5592 IV infusion is prepared as the time of use, but if necessary, the IV infusions may be prepared up to 18 hours prior to administration and stored at 2°C to 8°C refrigerated. The IV infusions should return to room temperature prior to administration.

MK-5592 IV will be given every 12 hours on Day 1, with infusions being not less than 9 hours or no more than 15 hours apart. The subsequent MK-5592 IV infusions will be administered once daily at approximately the same time every day with 24 hours apart, with infusions being not less than 21 hours or no more than 27 hours apart (infusions on Day 2 should not be less than 9 hours or no more than 15 hours apart). IV infusions should be administered for approximately 1.5 hours via a peripherally inserted central catheter or a dedicated lumen of a central venous catheter. Starting and stopping time of every infusion must be correctly recorded. Before and after infusion, investigator/sub-investigator will observe at the subject's infusion site.

If the dosing of study medication is delayed, the dose should be administered as soon as possible. Regarding the dose on or after Day 2, if it is more than 6 hours since the missed dose, the missed dose should be skipped and the next dose should be administered at the regularly scheduled time. Any missed doses should be properly documented in the subject's source documentation and eCRF.

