#### **7.1.2.8 Sample Collection for Plasma Concentration of MK-5592 (MK-5592 Treatment Arm)**

Blood sample for plasma concentration of MK-5592 is collected on the scheduled visit. Volume of the blood sampling is 2 mL/time. Blood sampling must be collected via other location different from the location of study administration. Regarding the sampling points of just before the end of first infusion on Day 1 and 8 for MK-5592 IV solution, blood sampling should be done before flushing. From the feasibility point of view, blood sampling after the treatment on Day 1 (IV solution: just before the end of first infusion, 6 to 10 hours after the initiation of the infusion and just before the treatment of second infusion, solid oral tablet: 2 to 4 hours after the first treatment, 6 to 10 hours after the treatment and just before the second treatment) can be performed after the second dosing if it is difficult to perform the blood sampling after the first dosing (e.g. in case that the first dose is in the night). If it is difficult to perform the blood sampling at the just before the second treatment/infusion, it may not be done but the reason for not performing the blood sampling must be recorded in the source document and eCRF. Blood sampling after the first dosing on Day 1 (or second dosing) should be performed at least 3 hours apart among these sampling points (IV solution: 6 to 10 hours after the initiation of the infusion and just before the treatment of second infusion, solid

oral tablet: 6 to 10 hours after the treatment and just before the second treatment). Sampling date and time must be correctly recorded in the source document and eCRF.

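### Flow chart footnote 6a contradicts itself on the second Day 1 IV pharmacokinetic sample: its list gives a pre-dose time where the rest of the protocol gives the end of the first infusion

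*Combined protocol and SAP*

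**What the plan says.** Three places in the protocol give the Day 1 sampling times for subjects who start on IV MK-5592.

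- **Section 6.0, footnote 6a, first sentence:** "Day 1;30 minutes before the treatment, just before the first treatment, 6 to 10 hours after the initiation of the infusion", and then a sample before the second infusion.
- **Section 6.0, footnote 6a, next sentence:** this allows the post-treatment samples to be moved to the second dose, and names them starting with "Blood sampling after the treatment on Day 1 (just before the end of first infusion".
- **Section 4.2.3.3:** "Thirty minutes before the treatment, just before the end of first infusion, 6 to 10 hours after the initiation of the infusion", and then a sample before the second infusion.
- **Section 7.1.2.8:** this gives a handling rule (draw before flushing) that begins "Regarding the sampling points of just before the end of first infusion on Day 1 and 8 for MK-5592 IV solution", and it repeats the end-of-first-infusion time when it lists the post-treatment samples.

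Sections 4.2.3.3 and 7.1.2.8 also require the 6-to-10-hour sample and the sample before the second dose to be spaced: "Blood sampling after the first dosing on Day 1 (or second dosing) should be performed at least 3 hours apart among these sampling points". Footnotes 6a (IV) and 7a (oral) do not repeat that rule.

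**The concern.** The first sentence of footnote 6a replaces an end-of-infusion sample with a second pre-dose sample, about half an hour after the first. Exclusion criterion 9(1) bars anyone who has already received MK-5592, so both pre-dose samples should contain no drug and the second adds essentially nothing.

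The location matters. Section 2.1 says that procedures and their prescribed times are outlined in the flow chart, and Section 7.1.5 points to it for visit requirements. Staff preparing a Day 1 draw can be expected to consult that list.

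At stake is the first-dose end-of-infusion concentration, which the sponsor chose to collect. The pharmacokinetic profile is secondary objective 5 and is to be analysed by population pharmacokinetics. A first-dose sample that was not drawn cannot be recovered later.

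**Working it through.** No figure in the plan needs reproducing. The check sets the passages side by side and counts samples.

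**Inputs**
- Sampling times: footnote 6a, Section 4.2.3.3 and Section 7.1.2.8, as quoted above.
- Infusion length: about 1.5 h (Section 5.2.1.1.1).
- Interval between the two Day 1 infusions: nominally 12 h, "with infusions being not less than 9 hours or no more than 15 hours apart" (Section 5.2.1.1.1).
- Remaining IV schedule: footnotes 6b and 6c.

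**Day 1 IV samples under each reading**

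| Sample | Footnote 6a, first sentence | Section 4.2.3.3 |
|---|---|---|
| 1 | 30 min pre-dose | 30 min pre-dose |
| 2 | just before first dose | just before end of first infusion (about 1.5 h) |
| 3 | 6–10 h | 6–10 h |
| 4 | before second infusion (9–15 h) | before second infusion (9–15 h) |
| Pre-dose / post-dose | 2 / 2 | 1 / 3 |

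The second sentence of footnote 6a and Section 7.1.2.8 each name the same three post-dose times as the right-hand column. The first sentence of footnote 6a therefore stands alone against its own next sentence and two other sections.

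**Size for one affected subject**
- Day 1 only: 1 of 4 samples is misplaced (1/4 = 25%), and post-dose samples fall from 3 to 2.
- Full schedule for a subject on IV throughout: 4 (Day 1) + 5 (Day 8 into Day 9) + 5 (Days 3, 14, 28, 42 and end of treatment) = 14. One misplaced sample is 1/14, or about 7%.
- The documents do not say how many subjects are expected to start on IV, so no trial-wide count can be given.

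**Spacing of samples 3 and 4 if only the flow chart is read**

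Gap = time of second dose − time of the 6-to-10-hour sample.
- Second dose at 12 h: 12 − 10 = 2 h up to 12 − 6 = 6 h.
- Second dose at 9 h: 9 − 6 = 3 h, down to about 9 − 9 = 0 h.
- With the 3-hour rule, sample 3 is due by 12 − 3 = 9 h in the first case and at 9 − 3 = 6 h in the second.

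The rule therefore bites in part of the allowed window. It is already stated in Sections 4.2.3.3 and 7.1.2.8.

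**What is untouched**

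Footnote 6c lists five Day 8/9 samples, including one just before the end of infusion. Section 4.2.3.3 describes the pharmacokinetic endpoint as the steady-state profile, which those samples serve.

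**The case against.** The strongest reply is that the intended design is not in doubt. The sentence straight after the faulty one names the end-of-first-infusion sample as the first of three post-treatment samples, so anyone who reads the whole footnote sees it. Section 7.1 calls the flow chart a summary and says the procedures are described in detail in what follows, and Section 2.1 also sends readers to Section 7.0 for detail. Section 7.1.2.8 names the time point twice. Section 7.1.3.2.1 says that sample-collection instructions are supplied separately, and these are not available here. Section 7.1.2.8 also requires actual sampling dates and times to be recorded, so a mistimed sample would be identifiable and could be modelled as what it is.

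Most of this stands, and it limits the consequence. A reader might infer that any site working from footnote 6a will draw two blanks and have no first-dose peak. The documents do not support that, because the footnote itself contains the correct time.

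A reader might also infer that a quarter of the Day 1 samples is lost, or half if the last two draws coincide. The first figure holds only at a site that follows the first sentence literally. The second also needs an early second dose and a late third sample, against a spacing rule stated twice elsewhere. It further counts the sample before the second dose as lost, although Section 7.1.2.8 lets sites omit that sample, with a recorded reason, when it is difficult to draw.

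Nor is the absence of the 3-hour rule from footnotes 6a and 7a an error in its own right. A summary need not repeat every rule.

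The reply does not remove the contradiction. The correct time appears in footnote 6a only within a provision for moving samples to the second dose, and the only complete and correct four-sample list is in the endpoint rationale. A site is left to decide which sentence governs.

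**Conclusion.** The inconsistency is certain. The first sentence of footnote 6a conflicts with its own second sentence and with Sections 4.2.3.3 and 7.1.2.8. It is a wrong sampling time in a schedule that sites use, not a flaw in the design.

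The consequence is a risk. Where the first sentence is followed literally, a subject starting on IV contributes two rather than three post-dose Day 1 concentrations, with none at the end of the first infusion. Day 8 is then the scheduled IV occasion with an end-of-infusion sample. For subjects who stop before the Day 8/9 samples, footnote 8 asks for that set only if possible. With actual times recorded, the effect is lost information about the first-dose peak rather than bias.

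This rests on two things the documents do not give: how many subjects start on IV, and whether the separate collection instructions carry the correct time. It would be too strong to say that the pharmacokinetic objective fails. The steady-state sampling is intact, and no primary safety or efficacy analysis uses the affected sample.

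**What to change.** Reconcile the first sentence of footnote 6a with Sections 4.2.3.3 and 7.1.2.8, so that the second Day 1 IV sample is due just before the end of the first infusion. Check that the separate sample-collection instructions say the same. Optionally, add a cross-reference in footnotes 6a and 7a to the existing 3-hour spacing rule.

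The cost is one corrected footnote and a short note to sites. It restores the sponsor's own schedule and adds no sample, visit or subject.
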